8.3 Study Assessments

A summary of both baseline and follow up assessments is outlined in Table 1 (adults) and Table 2 (children) below. If appropriate consent is in place the subjects may undertake any combination of any of the investigations listed in the investigation table at any of these visits.

Table 1: Summary of adult assessments

		COPD		Asthma			Pn	eumo	nia	He	art Fail	Healthy		
Time point	1a	1b	2	1a	1b	2	1a	1b	2	1a	1b	2	1a	2
Written Informed Consent	Χ			Χ			Χ			Χ			Χ	
Collection of demographic data (age, gender, height, weight,	Χ^		Χ^	Χ^		Χ^	Χ^		Χ^	Χ^		Χ^	Χ	Χ
ethnicity, smoking status)*														
Time of date of admission/discharge#	Χ^	Χ^		Χ^	Χ^		Χ^	Χ^		Χ^	Χ^			
Breathless Scores*														
Patient defined breathlessness	Χ^		Χ	Χ^		Χ	Χ^		Х	Χ^		Χ	Χ	Χ
Extended MRC dyspnoea score	Χ^		Χ^	Χ		Χ	Χ		Χ	Χ		Χ	Χ	Χ
New York Heart Association Dyspnoea Score (NYHA)										Χ^		X^		
100 mm visual analogue breathlessness score	Χ		Χ	Χ		Χ	Χ		Χ	Χ		Χ	Χ	Χ
Exacerbation history (previous health care utilisation and	Χ^		Χ^	Χ^		Χ^	Χ^		Χ^	Χ^		Χ^	Χ	Χ
acute use of medication)*														
Quality of breath VOCs questionnaire	Х	Χ	Χ	Χ	Χ	Χ	Χ	Χ	Х	Х	Χ	Χ	Χ	Х
Structured Clinical History of presenting complaint and past	Χ^		Χ^	Χ^		Χ^	Χ^		Χ^	Χ^		X^	Χ	Х
medical history*														1
Assessment of acute disease severity#*		•								•				
DECAF Score	Χ^													
CURB 65 Score							Χ^							
BTS Asthma Severity Score				Χ^										
Heart failure risk calculator										Χ^				
Concurrent medication usage	Χ^	χ^	Χ^	Χ^	Χ^	Χ^	Χ^	Χ^	Χ^	Χ^	Χ^	X^	Х	Х
12 lead ECG*	Χ^			Χ^			Χ^			Χ^				
Chest X-ray*	Χ^		Χ^	Χ^		Χ^	Χ^		Χ^	Χ^		Χ^		
Health Status Questionnaires*														
Asthma Quality of Life questionnaire (AQLQ)				Χ		Χ^								
COPD assessment tool (CAT)	Χ		Χ^											

		COPD		1	Asthma	a	Pneumonia			Hea	art Fail	Healthy		
	1a	1b	2	1a	1b	2	1a	1b	2	1a	1b	2	1a	2
NASA Task Load Index	Χ		Χ	Χ		Χ	Χ		Χ	Χ		Χ	Χ	X
Blood tests*														
BNP	Χ^		Χ	Χ			Χ			Χ^		Χ^	Χ	
Troponin-I	Χ			Χ			Χ			Χ^			Χ	
CRP	Χ^		Χ^	X^		X^	X^		X^	Χ^		Χ^	Χ)
Full blood count + differential count	Χ^		Χ^	Χ^		X^	X^		X^	Χ^		X^	Χ)
DNA and RNA (PAXGENE)~	Χ		Χ	Χ		Χ	Χ		Χ	Χ		Χ	Χ	7
Plasma and serum	Χ		Χ	Χ		Χ	Χ		Χ	Χ		Χ	Χ	- 7
Arterial or capillary blood gas*#	Χ^			Χ^			X^			Χ^				
Peripheral blood flow cytometry	Χ		Χ	Χ		Χ	Χ		Χ	Χ		Χ	Χ	
Lung function test		•												
Spirometry*	Χ^		Χ^	Χ^		Χ^							Χ	- 2
Oscillometry*	Χ		Χ	Χ		Χ	Χ		Χ	Χ		Χ	Χ	2
Exhaled nitric oxide (FeNO)				Χ		X^								
Sputum sample (spontaneous^ or induced)	Χ^		Χ	X^		Χ	X^		Χ	X^		Χ	Χ	
Volatile organic compounds (VOCs)	Χ	Χ	Χ	Х	Χ	Χ	Χ	Χ	Χ	Х	Χ	Χ	Χ	
Urine sample*	Χ		Χ	Χ		Χ	Χ		Χ	Χ		Χ	Χ	
Echocardiography*	Х									Χ^				
Quadriceps ultrasound	Х	Х	Х											
4 meter gait speed		Χ	Χ								Χ	Χ		
Review of Adverse Events & Serious Adverse Events		Χ	Χ		Χ	Х		Χ	Χ		Χ	Χ		7
Physical Exam*	χ^		Χ^	χ^		Χ^	Χ^		Χ^	χ^		Χ^	Х	

^{*}Can be performed at time points 1a or 1b. for healthy volunteers this can be completed at visit 1 or 2. For informed consent see protocol, ^ may be part of routine clinical care according to UHL Trust Guidelines. Arterial, capillary blood gases and blood cultures only done in selected clinical cases, # Acute patients only ~If DNA taken at time point 1a will not be repeated at timepoint 2.

Table 2: Summary of children assessments

essments		hood WI firmed A	Hea	thy	
Time point	1a	1b	2	1a	2
Written Informed Consent	Х			Х	
Collection of demographic data (age, gender, height, weight, ethnicity, smoking status)*	Χ^		Χ^	Х	Х
Time of date of admission/discharge#	Χ^	X^			
100 mm visual analogue breathlessness score*	Х		Х	Х	Х
Exacerbation history (previous health care utilisation and acute use of medication)*	Χ^		Χ^	Х	Х
Quality of breath VOCs questionnaire	Χ	Х	Χ	Х	Х
Structured Clinical History of presenting complaint and past medical history*	Χ^		Χ^	Х	Х
Concurrent medication usage	Χ^	Χ^	Χ^	Х	Х
Chest X-ray*	Χ^		Χ^		
Health Status Questionnaires*					
Asthma control questionnaire (ACQ)	Χ^		Χ^		
Asthma quality of life questionnaire (AQLQ)	Χ^		Χ^		
NASA Task Load Index	Х	Х	Х	Х	Х
Blood tests*+\$					
CRP	Χ^		Χ^	Х	Х
Full blood count + differential count	Χ^		Χ^	Х	Х
DNA and RNA (PAXGENE)	Х		Х	Х	Х
Plasma and serum	Х		Х	Х	Х
Arterial or capillary blood gas*	Χ^				
Blood culture*	Χ^				
Lung function test					
Spirometry*	Χ^		Χ^	Х	Х
Exhaled nitric oxide (FeNO)	Х		Х	Х	Х
Sputum sample (spontaneous^ or induced)\$	Χ^		Χ^	Х	Х
Volatile organic compounds (VOCs)	Х	Х	Х	Х	Х
Urine sample*	Х		Х	Х	Х
Review of Adverse Events & Serious Adverse Events		Х	Х		Х
Physical Exam*	Χ^		Χ^	Х	Х

^{*}Can be performed at time points 1a or 1b. For informed consent see protocol, ^ Part of routine clinical care as part of the University Hospitals of Leicester, acute care clinical pathway. Will be performed in selected clinical cases based on clinical need, # Acute patients only, + up to 35 mls maximum per visit, ⁵ optional

A description of the research assessments is outlined below

Demographics

All standard clinical demographics routinely recorded in acutely unwell patients will be captured using study specific case report forms (CRFs). These will include the age, sex, height, weight, smoking status and ethnicity of the patient.

Medical History

All standard clinical data routinely recorded in acutely unwell patients will be captured using study specific case report forms (CRFs). This will include co morbidities usually supplied with the GP referral letter and the use of hospital clinical information systems such as ICE to cross check co morbidities where necessary using discharge summaries as well as case notes review.

• Concomitant Medication

Current medication will be collected. This will comprise of usual medication, medication in the two weeks prior to visit 1a. In the case of admission, additional confirmation will be performed after standard pharmacy review by the admissions pharmacist allocated to the admissions unit in question.

• Physical Examination

All standard clinical data routinely recorded in acutely unwell patients will be captured using study specific electronic case report forms (CRFs). Standard clinical examination findings relevant to the indicator diagnosis in question will be recording and will include pulse, blood pressure, temperature, respiratory rate, oxygen saturations and impairment of cognition.

• Collection and recording of standard clinical care pathway diagnostic

The majority of acute care admissions with undifferentiated breathlessness will undergo various combinations of the following assessments dependent upon their admission diagnosis.

- Chest x ray
- 12 lead ECG
- Laboratory blood tests may include: Urea and electrolytes, liver function tests, albumin, corrected calcium,phosphate, D-Dimer, BNP, Troponin-I, full blood count, haematocrit and differential white cell count.
- Additional investigation such echocardiography (will be done during acute admission between time points 1a and 1b). Echo will measure LV and RV function, LA size, vavular function, LV wall thickness and e/e' on tissue Doppler.
- **The responsibility to act upon and record abnormal investigations within the patient's clinical notes will remain with the admitting clinical team who will have ordered and requested the investigations.
 - Breath sampling procedures (PLEASE REFER TO APPENDIX D: ASSET ALLOCATION APPENDIX FOR A
 DETAILED SUMMARY OF THE CORE BREATH DETECTION TECHNOLOGIES)

Breath sampling will be performed using various combinations of the devices below dependent upon patient location, level of illness (acuity) and phase of the program (discovery/replication). Breath sampling will be limited to a duration acceptable to a patient (typically 30 mins) at any particular study visit to minimise disruption to the patient care pathway and flow.

Advion CMS: Discovery Phase (Phase 1) Breath Analysis:

The Advion Expression compact mass spectrometer (CMS) is a single quadrupole mass spectrometer that enables the study of volatiles in breath by adding a simple modification at the front end of the instrument. The volatiles are drawn into the mass spectrometer ion source directly from the patient's breath using a Venturi pump. This pump creates a Venturi effect sucking the volatiles into the mass spectrometer at a rate of approximately 300 mL/min. When sampling, patients wear a facemask which is fed with approximately 35 l/min of purified air to which the Venturi pump inlet is connected. The extracted breath samples pass through a transfer line heated to an optimal temperature to avoid condensation of the volatiles. The minimum time required to perform a breath sample is 2 min. After this sampling time the data can be extracted immediately for analysis.

GC-IMS (B&S Analytiks): Replication Phase (Phases 2) Breath Analysis:

Gas chromatography ion mobility spectrometry (GC-IMS) enables the detection of VOCs in exhaled breath of patients in trace gas concentrations (ng/L-pg/L range). Sampling takes place using a Spiroscout spirometer. The patients exhale through a disposable mouth piece connected to a Teflon tube. A piezoelectric pressure sensor is used to monitor the breathing profile, this opens the sampling valve at the appropriate point in the breath profile to collect end-tidal breath in a sample loop of 10 mL volume. After filling this loop, the collected sample air is then transferred to a multicapillary column for a chromatographic separation, which is achieved in 12 min. The separated molecules are then transferred into the IMS, ionised and then separated according to their mobility in a weak electric field.

GC-FAIMS (Owlstone Nanotech Ltd): Replication Phase (Phase 2) Breath analysis:

Gas chromatography field asymmetric ion mobility spectrometry (GC-FAIMS) is a gas detection technology that separates and identifies chemical ions based on their mobility under a varying electric fields at atmospheric pressure. Samples are collected on adsorbent tubes (Tenax/Carbograph) using a CE marked handheld sampling device. Samples are then extracted from tubes using thermal desorption and then analysed by GC-FAIMS. The combination of the high selectivity of GC with the high sensitivity of FAIMS enables the detection of volatiles in a wide range of matrices such as aqueous, solid and gaseous. FAIMS is also known as differential mobility spectrometry (DMS).

Real time breath monitoring using proton transfer reaction time of flight mass spectrometry (PTR-ToF-MS):

In order to sample a patient's breath using this technique, two breath sampling devices will be used. The first device is a Loccioni SOFIA GSI-S; the subject is required to exhale a single breath, five times (three if providing five samples proves too difficult) into a sterile mouthpiece connected to an electrostatic bacterial/viral filter whilst wearing a nose clip (all CE marked). Flow from the mouthpiece passes into a gas sampling interface capnograph (Loccioni GSI-S – CE marked) and real-time user feedback of flow is provided on screen, allowing the regulation of the breath sampling rate. The gas sampling interface acts to simultaneously trigger the acquisition of the PTR-ToF-MS data and the exhaled breath travels through the capnograph down a heated sample line into the ion source of the PTR-ToF-MS

The second breath sampling device is a ReCIVA breath sampler (Owlstone), as described in Section 6.2, with one of the adsorbent Tenax tubes replaced with an outlet tube adapted for online sampling. The exhaled breath is transferred to the PTR-ToF-MS via a heated transfer line connected to the outlet tube, continuously drawn at a constant flow rate by the PTR-ToF-MS. The online adaptation of the consumable adsorbent tube does not affect the CE mark of the ReCIVA sampling device.

Page 28 of 46

Once the breath sample reaches the PTR-ToF-MS, via either breath sampler, the breath mixes with protonated water (H_3O^*) inducing proton transfer to the target volatile organic compounds (VOCs) present, resulting in their ionisation. Sample ions are then guided into the time of flight mass spectrometer and mass spectra, showing the abundance and mass of the VOCs present, are collected throughout the exhalation. Following sampling, mouthpieces, filters and nose clips are disposed of and all patient contacted surfaces wiped down with antiseptic cleaning wipes in preparation for the next patient.

Sputum collection

Spontaneous or induced sputum samples can be collected. In the case of induced sputum sample collection all subjects will have a baseline FEV_1 measured. Sputum collection will be collected using the principles as defined by the European Respiratory Society Guidelines. All equipment used for performing the following procedure will be de-contaminated according to local working instructions. The procedure may be stopped prematurely if: (1) the subject's FEV_1 drops by greater than 20% of the post-salbutamol FEV_1 baseline value, (2) the subject feels any discomfort and does not want to continue with saline inhalation procedure or (3) the investigator feels that it is unsafe to continue with the saline inhalation. Sputum supernatants will be stored at the investigative site in dedicated -80 C freezers.

Urine Collection

Urine will be collected from subjects. It will be collected into a suitable container and stored at the investigative site in dedicated -80 C freezers.

Lung function

Lung function testing will include spirometry (pre and post bronchodilator), FeNO (Fraction exhaled Nitric Oxide), hand held oscillometry (adults asthma patients only). Peak flow measurements (to be recorded as part of routine care in asthmatics), and volatile breath analysis. All of these are non-invasive clinical tests.

• Research Echocardiography (ECHO)

For patients (excluding healthy volunteers) where there is no clinical indication for ECHO a research ECHO will be performed by a certified technician following written informed consent from the patient any time point between visit 1a and visit 1b.

Blood sampling

In addition to the routine clinical blood samples will be taken for RNA and DNA, serum and plasma, peripheral blood cell flow cytometry analysis per visit. This may total up to 85 mls for an adult and 35mls for a child. Samples will be barcoded and stored at the investigative site in dedicated -80 C freezers. Samples may be transferred to the NIHR national bio sample centre subject to available funding. Blood samples will be taken at the same time point as the clinical samples to minimise inconvenience to the patient.

• Health Questionnaires

Questionnaires regarding the subjects' health and disease status will be completed. These will include measures of health status.

NASA Task Load Index

It is a widely used, subjective, multidimensional assessment tool that rates perceived workload in order to assess a task, system, or team's effectiveness or other aspects of performance. It assesses work load on five 7-point scales including mental demand, physical demand, temporal demand, performance, effort and Page 29 of 46

frustration. Increments of high, medium and low estimates for each point result in 21 gradations on the scales. This tool will be incorporated into EMBER to assess the overall performance and feasibility of using ReCIVA mask in breath collection.

• Physical performance

4 meter gait speed (the time it takes to walk 4 meters) and quadriceps size measured using ultrasound will be performed to assess physical performance in selected patients. Both are measures of frailty, non-invasive, and validated in the acute care setting in chronic respiratory disease. If ultrasound measure is missed at timepoint 1 then it will not be taken at timepoint 2.

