6 STUDY DESIGN

6.1 Summary of Trial Design

The clinical study will be a prospective observational study across two acute clinical sites that routinely assess and treat cardio-respiratory admissions due to breathlessness within Leicester.

- (i) Glenfield Hospital (GGH): Adult cardio-respiratory presentations to Glenfield Hospital (including Clinical Decisions Unit (CDU) & inpatient wards), outpatient clinics and NIHR Leicester Biomedical Research Centre (BRC)
- (ii) Leicester Royal Infirmary: Adult and paediatric cardio-respiratory presentations to A&E, Children's Assessment Unit (CAU), Diagnostics Development Unit (DDU), inpatient wards, outpatient clinics and Research Space

Follow up and stable state controls will be assessed in the outpatient setting within University Hospitals of Leicester including the BRC. The study flow is summarised in Figure 1 below.

[figure not shown]

Fig 1: Study flow chart. Figure demonstrates the patient journey from admission through to outcome. Assessments carried out at

Figure 1: Study Flow chart

Prospective participants with self reported acute breathlessness, either requiring admission or a change in baseline treatment, presenting within UHL. The streaming and care pathways at UHL allocate ambulance admissions to the two units described above with appropriate clinical care being provided at each site according to national guidelines and local protocols / policies.

Patients with confirmed acute airwary exacerbation or heart failure decompensation as part of other research studies at the NIHR Leicester BRC may also be included.

Age- and/or home environment matched adult/spousal/parent and sibling healthy volunteers will be recruited where possible on the admissions unit and when not possible in the research units across both sites at a separate visit. All attempts will be made to sample breath on at least two of the same time points as patients within these disease groups, however sampling may occur in a different location and at different serial time points. All healthy volunteers will complete a range of questionnaires adapted from generic cohort studies to characterise their diet, lifestyle and environmental exposures. A stable state control population will also be recruited to compare with the unstable state. This will consist of participants with a confirmed diagnosis matched with the acute care population but not in the exacerbation state.

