A standard definition for acute breathlessness does not exist. We will use the presence of patient reported acute breathlessness, above their usual baseline breathlessness (i.e. in stable state) as a binary variable. We will also use the extended MRC score, and 100mm visual analogue score (VAS), as a continuous variable.

The extended MRC score has been validated in chronic disease populations, including in the acute state, and may be applied to diseases other than COPD where originaly validated. We will define a change in breathlessness of the eMRC as at least a unit change from stable state. In addition a VAS score will be used to measure breathlessness.

Definition of Post Exacerbation Recovery

Patient recovery will be defined as

- (i) Patient reported recovery from the acute exacerbation spell and back to their baseline extended MRC score or clinician defined recovery from the acute exacerbation spell and
- (ii) At least 6 weeks post exacerbation event (up to 6 months).
 - 6.2 Summary of Additional Assessment and breath sampling procedures/ devices

A number of analytical devices will be utilised to sample breath in acutely ill patients and based upon the (i) clinical site, (ii) operational needs and likely patient grouping (severity of underlying condition at the point of admission) within each clinical site, (iii) balance of discovery and point of care sensing technologies: breath sensors will be co-located to the two EMBER acute admissions units. All devices will be maintained to a high level of operational readiness by the technicians and device specialists within the clinical operations group. All devices will be checked for safety by Medical Physics at University Hospitals of Leicester NHS Trust.

[figure not shown]
The following devices will be utilised to evaluate breath volatile organic compounds

Page 18 of 46

- A portable mass spectroscopy device (Advion Ltd) for discovery based metabolomic breath sampling. This device is also capable of real time sampling.
- A proton transfer mass spectroscopy device (PTRMS) for discovery based metabolomic breath sampling.
- A point of care GC-FAIMS Lonestar device (Owlstone Nanotech Ltd)
- A point of care linear IMS Bioscout device (Owlstone Ltd: GC-FAIMS Lonestar analyser)

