A CE marked breath sampling device developed by Owlstone Nanotech Ltd (Appendix A) will be used to sample breath in the majority of patients onto adsorbent Tenax tubes as well as acquiring online sampling. This effectively allows de coupling of the breath sampling from the breath sensor and analysis platforms in selected patients and allows patients that are not able to be mobilised in a chair to a real time breath sampling device to be sampled at their bedside. The Owlstone RECIVA sampler (Figure 3) is capable of entraining oxygen and is therefore suitable for patients in respiratory failure requiring low to moderate flow rates of oxygen to maintain target oxygen saturations. CE marking approvals are appended to this protocol in (Appendix B).

Figure 2: Owlstone CE Marked Breath Sampler

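### Breath sampler and device may vary with acuity, place and site, but the models in 10.1 list neither sampler nor site and no platform is named for the primary analysis, so a sampler difference can pass for a biomarker effect

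*Protocol*

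**What the plan says.** Three places in the protocol govern how breath is sampled.

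- Section 8.3 (breath sampling procedures) allows "various combinations of the devices below dependent upon patient location, level of illness (acuity) and phase of the program".
- Section 6.2 places devices according to clinical site, operational needs and "likely patient grouping (severity of underlying condition at the point of admission) within each clinical site". It adds that the ReCIVA mask "allows patients that are not able to be mobilised in a chair to a real time breath sampling device to be sampled at their bedside". This mask "will be used to sample breath in the majority of patients onto adsorbent Tenax tubes".
- The PTR-ToF-MS text in 8.3 states: "In order to sample a patient's breath using this technique, two breath sampling devices will be used". The first is a mouthpiece interface taking single exhalations, five of them or "three if providing five samples proves too difficult". The second is the ReCIVA mask, drawn continuously at constant flow. The text continues: "Once the breath sample reaches the PTR-ToF-MS, via either breath sampler".

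Section 6.1 fixes the place of later visits: "Follow up and stable state controls will be assessed in the outpatient setting within University Hospitals of Leicester including the BRC". It also allows healthy volunteers to be sampled in a different location from patients.

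In 10.1 the primary outcome has two levels, acute breathlessness and recovery. The listed covariates are age, sex, blood eosinophils, BNP, CRP, troponin-I, canonical VOCs and, where relevant, a comorbidity score. The disease-class model lists age, sex, comorbidity scores, disease risk scores and acute treatments, to be included where they improve fit. The repeated-measures model has a random intercept and a random effect for time. None of these lists has a sampler, instrument or site term, and the primary analysis names no platform.

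**The concern.** The way breath is measured is allowed to depend on the state being compared. Acuity differs between acute and recovery by definition. Place differs too, since acute samples come mainly from admission units and wards and recovery samples from outpatient settings. Two of the three drivers of device choice in 8.3 therefore run along the primary contrast, and severity may also differ between disease classes.

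If samplers differ systematically in what they deliver to an instrument, and the model has no term for the sampler, the difference is attributed to acute state or diagnosis. The result would be a VOC that looks diagnostic but reflects how the breath was collected. Analysis alone cannot fully repair this if the same patient was sampled one way at visit 1a and another way at visit 2.

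**Working it through.** The protocol states no sampler offset and no split of sampler use, so there is no figure of its own to reproduce. The check has two parts.

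**1. Where the route is open**

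| Instrument | Breath interface described | Can samplers mix within the instrument? |
|---|---|---|
| Advion CMS | its own facemask | not as described |
| GC-IMS | spirometer mouthpiece | not as described |
| GC-FAIMS | handheld tube sampler | not as described |
| PTR-ToF-MS | mouthpiece interface or ReCIVA | yes |

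Separate analysis by instrument therefore holds the sampler constant on the first three, but not on PTR-ToF-MS. Place still differs between acute and recovery on every instrument. The interim GC-MS panel was not background subtracted (21.2), so ambient air is not removed there either.

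**2. Size, on assumed inputs**

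From the protocol: 4 acute adult classes × 55 in discovery (21.5) = 220 patients; 5% significance level (10.3), taken as two-sided. Assumed: sampler offset 0.5 SD; correlation 0.5 between visits; all 220 patients complete as pairs on one instrument; difference in use of one sampler between acute and recovery of 10, 20 or 40 points (for example 90% against 80%, 40% against 20%, 60% against 20%).

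- False shift = offset × difference in use.
- SE of the mean paired difference = √(2 × (1 − 0.5) / 220) = 0.0674 SD.
- Rejection probability = Φ(z − 1.96) + Φ(−z − 1.96), with z = shift / SE.

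| Difference in use | False shift | z | Null VOC with p<0.05 |
|---|---|---|---|
| 10 points | 0.5 × 0.10 = 0.05 SD | 0.74 | about 11% |
| 20 points | 0.5 × 0.20 = 0.10 SD | 1.48 | 32% |
| 40 points | 0.5 × 0.40 = 0.20 SD | 2.97 | 84% |

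This SE leaves out the extra spread that mixed samplers create. If the sampler is chosen independently at the two visits, the 40-point case has variance 1 + 0.25 × (0.6 × 0.4 + 0.2 × 0.8) = 1.10, SE √(1.10/220) = 0.0707, z = 2.83 and rejection about 81%, so the picture hardly changes.

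A second check used 1,000 simulated logistic regressions per setting, with 220 acute and 220 recovery samples treated as independent and a 0.5 SD offset. Without a device term, false positives were 17%, 32% and 73% at differences of 20, 30 and 50 points, with spurious odds ratios of 1.10, 1.15 and 1.28. With no difference in use the rate stayed near 5%. With a device term it was 3% to 6% in every setting run, including offsets of 1 SD.

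As a yardstick, the odds ratio of 1.2 that the study is sized on (21.2), read as per SD, corresponds to a shift of about ln 1.2 = 0.18 SD. A 0.5 SD offset produces that at a difference in use of 0.18 / 0.5 = 36 points.

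**The case against.** The best case against runs as follows.

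- **There is a common sampler.** The steps for all sites in 6.1 specify a standardised face mask as well as real-time sampling, and 6.2 has the mask used in most patients. A bedside patient may simply lack the additional real-time reading, which is missing data and not a change of sampler. This stands in part: an analysis confined to ReCIVA tubes would hold the sampler constant. The protocol does not commit to that, and place would still differ.
- **The PTR-ToF-MS text can mean that every patient uses both samplers.** That reading is open. The wording that breath arrives through either one fits both readings, and nothing says that acuity decides between them.
- **Detailed methods are deferred.** Section 10.1 points to a separate data analysis plan, which may handle platforms, and the class-model covariates are conditional on fit. Hence the omission can be asserted only of the protocol. Which sampler is used at visit 2 is nevertheless a matter of conduct that a later analysis plan cannot put right.
- **The percentages rest on chosen inputs.** This is correct. Low mask use at recovery, such as 20%, fits poorly with use in the majority of patients; 90% against 80% fits better and gives the 11% figure. Complete pairing is also optimistic, since 9.1.5 expects 14% mortality at 3 months in COPD.

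A reader might infer more than the text supports: that device differences certainly load onto the contrasts, that separate analysis by instrument never helps, that phase also confounds, or that the artefact must recur in replication. Bias needs samplers mixed in one model and used unequally, and the protocol states neither. Separate analysis does hold the sampler constant on single-sampler instruments. Phase cannot confound a contrast made within one phase. Because 8.3 assigns some instruments to discovery and others to replication, an offset on one need not reappear on another.

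**Conclusion.** The point holds as a possible route for measurement bias, not as demonstrated bias. The protocol ties sampler and device choice to acuity, location and site, lists covariates without sampler or site, and names no platform for the primary analysis. The exposure is clearest on PTR-ToF-MS. For other instruments the remaining issue is place of sampling.

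The size is unknown. The range of about 11% to 84% false positives for a null VOC is illustrative and depends on an assumed 0.5 SD offset, a 10 to 40 point difference in use, 220 complete pairs and a correlation of 0.5. With equal sampler use the inflation disappears. The change is worth making because it is cheap and some of it must be in place before visit 2 samples are taken.

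**What to change.** 1. Name the instrument and sampler for the primary analysis, for example ReCIVA onto Tenax tubes with GC-MS, since 6.2 makes that the most widely used sampler.
2. Instruct that visit 2 uses the same sampler as visit 1a, and record the sampler at each visit.
3. Analyse each instrument separately and do not pool readings across instruments.
4. In the adult acute-versus-healthy and disease-class models, include site as a factor, and sampler wherever more than one feeds the instrument.
5. Report the acute-recovery contrast in patients with the same sampler at both visits as a sensitivity analysis. It should not be the main analysis, because it may drop the patients too ill to be moved.
6. State as limitations that site cannot be separated from the paediatric class, whose presentations 6.1 lists only at Leicester Royal Infirmary, and that a site term does not remove the ward-to-outpatient difference built into acute against recovery.

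The cost is slightly more analysis work, a scheduling constraint at visit 2 and fewer pairs in the sensitivity analysis.
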